## 10.6 Appendix 13: Abbreviations

ADHD	attention deficit hyperactivity disorder
AE	adverse event
AESI	adverse event of special interest
CRF	case report form
CT	computerised tomography
CTR	clinical trial report
DFU	directions for use
DUN	dispensing unit number
ECG	electrocardiogram
eCRF	electronic case report form
FAS	full analysis set
FDAAA	the Food and Drug Administration Amendments Act
FSH	follicle-stimulating hormone
GCP	Good Clinical Practice
GH	growth hormone
GHD	growth hormone deficiency
HbA1c	glycated haemoglobin
hGH	human growth hormone
HV	height velocity
IB	Investigator Brochure
ICH	International Council for Harmonisation
IEC	independent ethics committee
IGF-I	insulin-like growth factor I
IGF BP-3	insulin-like growth factor binding protein 3
IMP	investigational medicinal product
IRB	institutional review board
IWRS	interactive web response system
LAR	legally acceptable representative
MAR	missing at random

MMRM	mixed model for repeated measurements
MRI	magnetic resonance imaging
PCD	primary completion date
PD	pharmacodynamics
PK	pharmacokinetics
PP	per protocol analysis set
PRO	patient reported outcome
SAE	serious adverse event
SAP	statistical analysis plan
SAS	safety analysis set
s.c	subcutaneous
SDS	standard deviation score
SGA	small for gestational age
SMPC	summary of product characteristics
SUSAR	suspected unexpected serious adverse reaction
TMM	trial materials manual

## 10.7 Appendix 14: Dose tables for Norditropin® and somapacitan

### Norditropin® FlexPro®:

0.034 mg/kg Norditropin® FlexPro® 10 mg/1.5 ml	
Weight interval (kg)	Dose (mg)
5.0-5.1	0.15
5.2-6.6	0.20
6.7-8.0	0.25
8.1-9.5	0.30
9.6-11.0	0.35
11.1-12.4	0.40
12.5-13.9	0.45
14.0-15.4	0.50
15.5-16.9	0.55
17.0-18.3	0.60
18.4-19.8	0.65
19.9-21.3	0.70
21.4-22.7	0.75
22.8-24.2	0.80
24.3-25.7	0.85
25.8-27.2	0.90
27.3-28.6	0.95
28.7-30.1	1.00
30.2-31.6	1.05
31.7-33.0	1.10
33.1-34.5	1.15
34.6-36.0	1.20
36.1-37.4	1.25
37.5-38.9	1.30
39.0-40.4	1.35
40.5-41.9	1.40
42.0-43.3	1.45
43.4-44.8	1.50
44.9-46.3	1.55

0.034 mg/kg Norditropin® FlexPro® 10 mg/1.5 ml	
Weight interval (kg)	
Dose (mg)	
46.4-47.7	1.60
47.8-49.2	1.65
49.3-50.7	1.70
50.8-52.2	1.75
52.3-53.6	1.80
53.7-55.1	1.85
55.2-56.6	1.90
56.7-58.0	1.95
58.1-59.5	2.00
59.6-61.0	2.05
61.1-62.4	2.10
62.5-63.9	2.15
64.0-65.4	2.20
65.5-66.9	2.25
67.0-68.3	2.30
68.4-69.8	2.35
69.9-70.0	2.40

**Somapacitan:**

0.16 mg/kg	
Somapacitan 5 mg/1.5 ml	
Weight interval (kg)	Dose (mg)
5.0-5.1	0.80
5.2-5.4	0.85
5.5-5.7	0.90
5.8-6.0	0.95
6.1-6.4	1.00
6.5-6.7	1.05
6.8-7.0	1.10
7.1-7.3	1.15
7.4-7.6	1.20
7.7-7.9	1.25
8.0-8.2	1.30
8.3-8.5	1.35
8.6-8.9	1.40
9.0-9.2	1.45
9.3-9.5	1.50
9.6-9.8	1.55
9.9-10.1	1.60
10.2-10.4	1.65
10.5-10.7	1.70
10.8-11.0	1.75
11.1-11.4	1.80
11.5-11.7	1.85
11.8-12.0	1.90
12.1-12.3	1.95
12.4-12.5	2.00

0.16 mg/kg Somapacitan 10 mg/1.5 ml	
Weight interval (kg)	
Dose (mg)	
10.5-10.7	1.70
10.8-11.0	1.75
11.1-11.4	1.80
11.5-11.7	1.85
11.8-12.0	1.90
12.1-12.3	1.95
12.4-12.6	2.00
12.7-12.9	2.05
13.0-13.2	2.10
13.3-13.5	2.15
13.6-13.9	2.20
14.0-14.2	2.25
14.3-14.5	2.30
14.6-14.8	2.35
14.9-15.1	2.40
15.2-15.4	2.45
15.5-15.7	2.50
15.8-16.0	2.55
16.1-16.4	2.60
16.5-16.7	2.65
16.8-17.0	2.70
17.1-17.3	2.75
17.4-17.6	2.80
17.7-17.9	2.85
18.0-18.2	2.90
18.3-18.5	2.95
18.6-18.9	3.00
19.0-19.2	3.05
19.3-19.5	3.10
19.6-19.8	3.15
19.9-20.1	3.20
20.2-20.4	3.25
20.5-20.7	3.30
20.8-21.0	3.35

0.16 mg/kg Somapacitan 10 mg/1.5 ml	
Weight interval (kg)	
Dose (mg)	
21.1-21.4	3.40
21.5-21.7	3.45
21.8-22.0	3.50
22.1-22.3	3.55
22.4-22.6	3.60
22.7-22.9	3.65
23.0-23.2	3.70
23.3-23.5	3.75
23.6-23.9	3.80
24.0-24.2	3.85
24.3-24.5	3.90
24.6-24.8	3.95
24.9-25.0	4.00

0.16 mg/kg Somapacitan 15 mg/1.5 ml	
Weight interval (kg)	Dose (mg)
16.0-16.5	2.6
16.6-17.1	2.7
17.2-17.8	2.8
17.9-18.4	2.9
18.5-19.0	3.0
19.1-19.6	3.1
19.7-20.3	3.2
20.4-20.9	3.3
21.0-21.5	3.4
21.6-22.1	3.5
22.2-22.8	3.6
22.9-23.4	3.7
23.5-24.0	3.8
24.1-24.6	3.9
24.7-25.3	4.0
25.4-25.9	4.1
26.0-26.5	4.2
26.6-27.1	4.3
27.2-27.8	4.4
27.9-28.4	4.5
28.5-29.0	4.6
29.1-29.6	4.7
29.7-30.3	4.8
30.4-30.9	4.9
31.0-31.5	5.0
31.6-32.1	5.1
32.2-32.8	5.2
32.9-33.4	5.3
33.5-34.0	5.4
34.1-34.6	5.5
34.7-35.3	5.6
35.4-35.9	5.7
36.0-36.5	5.8
36.6-37.1	5.9

0.16 mg/kg Somapacitan 15 mg/1.5 ml	
Weight interval (kg)	Dose (mg)
37.2-37.8	6.0
37.9-38.4	6.1
38.5-39.0	6.2
39.1-39.6	6.3
39.7-40.3	6.4
40.4-40.9	6.5
41.0-41.5	6.6
41.6-42.1	6.7
42.2-42.8	6.8
42.9-43.4	6.9
43.5-44.0	7.0
44.1-44.6	7.1
44.7-45.3	7.2
45.4-45.9	7.3
46.0-46.5	7.4
46.6-47.1	7.5
47.2-47.8	7.6
47.9-48.4	7.7
48.5-49.0	7.8
49.1-49.6	7.9
49.7-50.3	8.0
Split dose	Split dose
50.4-50.9	8.1
51.0-51.5	8.2
51.6-52.1	8.3
52.2-52.8	8.4
52.9-53.4	8.5
53.5-54.0	8.6
54.1-54.6	8.7
54.7-55.3	8.8
55.4-55.9	8.9
56.0-56.5	9.0
56.6-57.1	9.1
57.2-57.8	9.2

0.16 mg/kg Somapacitan 15 mg/1.5 ml	
Weight interval (kg)	
Dose (mg)	
57.9-58.4	9.3
58.5-59.0	9.4
59.1-59.6	9.5
59.7-60.3	9.6
60.4-60.9	9.7
61.0-61.5	9.8
61.6-62.1	9.9
62.2-62.8	10.0
62.9-63.4	10.1
63.5-64.0	10.2
64.1-64.6	10.3
64.7-65.3	10.4
65.4-65.9	10.5
66.0-66.5	10.6
66.6-67.1	10.7
67.2-67.8	10.8
67.9-68.4	10.9
68.5-69.0	11.0
69.1-69.6	11.1
69.7-70.0	11.2

## **10.8 Appendix 15: Protocol amendment history**

The Protocol amendment summary of changes table for the current protocol version is located directly before the table of contents.

**Protocol version X, including version(s) Y and Z: (date), global/country**

**Overall rationale for preparing protocol version X**

Section # and name	Description of change	Brief rationale

## Version History

This Statistical Analysis Plan (SAP) for study NN8640-4468 is based on the protocol version 1.0 dated 01 July 2020.

SAP Version	Date	Change	Rationale
1.0	28 April 2023	Not Applicable	Original version
2.0	15 December 2023	Section 4.3.2: Secondary endpoints, height SDS	As Chinese standards data did not have monthly LMS values, they were calculated using the available reference data. SAP has been updated by describing the methodology used to calculate monthly LMS values. Height SDS was then calculated using these derived LMS values. No changes were made to primary analysis.

**List of abbreviations**

ADHD	attention deficit hyperactivity disorder
AE	adverse event
AESI	adverse event of special interest
ANCOVA	analysis of covariance
CI	confidence interval
CTR	clinical trial report
ECG	electrocardiogram
FAS	full analysis set
FDAAA	the Food and Drug Administration Amendments Act
GH	growth hormone
GHD	growth hormone deficiency
HbA1c	glycated haemoglobin
hGH	human growth hormone
HV	height velocity
ICH	International Council on Harmonization
IGF-I	insulin-like growth factor I
IGF BP-3	insulin-like growth factor binding protein 3
MAR	missing at random
MedDRA	medical dictionary for regulatory activities
MMRM	mixed model for repeated measurements
PD	pharmacodynamics

PK	pharmacokinetics
PP	per protocol analysis set
PRO	patient reported outcome
SAE	serious adverse event
SAP	Statistical Analysis Plan
SAS	safety analysis set
SDS	standard deviation score
TFL	tables, figures and listings

## 1 Introduction

Primary analysis of the primary endpoint addressing the primary estimand was defined in protocol before first patient first visit (FPFV). There are no changes to the analysis described in the protocol.

This SAP is based on the protocol: *A trial comparing the efficacy and safety of once weekly dosing of somapacitan with daily Norditropin® in Chinese children with growth hormone deficiency*. REAL 6, version 1.0 (dated 01 July 2020). This SAP covers specification of statistical considerations and analyses for efficacy and safety data. SAP 1.0 was created prior to unblinding but post FPFV. Sensitivity analysis of primary endpoint has been included to investigate possible impact of delayed visits due to COVID.

### 1.1 Objectives, Endpoints, and Estimands

#### 1.1.1 Primary objective:

To compare efficacy of somapacitan vs Norditropin® on longitudinal growth in Chinese children with GHD.

#### 1.1.2 Secondary objective:

To compare safety of somapacitan vs Norditropin® in Chinese children with GHD

#### 1.1.3 Primary endpoint

**Table 1 Primary endpoint**

Endpoint title	Time frame	Unit
Height Velocity	Height velocity (annualised) at week 52	cm / year

#### 1.1.4 Secondary endpoints

##### 1.1.4.1 Supportive secondary endpoints

**Table 2 Supportive secondary: Efficacy endpoints**

Endpoint title	Time frame	Unit
Change in bone age	From visit 1 to week 52	Years
Change in Height Standard Deviation Score	From baseline (week 0) to week 52	-10 to +10

Change in Height Velocity Standard Deviation Score	From baseline (week 0) to week 52	-10 to +10
--	-----------------------------------	------------

**Table 3 Supportive secondary: Safety endpoints**

Endpoint title	Time frame	Unit
Change in fasting plasma glucose	From baseline (week 0) to week 52	mmol/l
Change in HbA1c	From baseline (week 0) to week 52	%

**Table 4 Supportive secondary: Pharmacodynamics**

Endpoint title	Time frame	Unit
Change in IGF-I Standard Deviation Score	From baseline (week 0) to week 52	-10 to +10
Change in IGFBP-3 Standard Deviation Score	From baseline (week 0) to week 52	-10 to +10

### 1.1.5 Primary estimand

**Hypothetical strategy** - ancillary therapy not available: The treatment difference between somapacitan and Norditropin® in mean annualised HV at week 52 if ancillary therapy had not been available prior to week 52 (i.e. assuming no initiation of ancillary therapy) in children with GHD. The use of ancillary therapy may lead to attenuation of the treatment effect of interest or even exaggerate the treatment effect and the estimand thus aims to reflect the treatment difference attributable to the initially randomised treatments.

### 1.2 Study Design

A randomised open-labelled two arm phase 3 trial designed to confirm non-inferiority of efficacy and investigate safety of once weekly subcutaneous treatment of somapacitan compared to daily subcutaneous growth hormone (Norditropin®) treatment in Chinese prepubertal children with growth hormone deficiency.

[figure not shown]
The total trial duration for a subject will be up to 70 weeks approximately.

The trial duration includes a 2 to 14 weeks of screening period, a 52 weeks of treatment period and a minimum 30 days of follow up period.

Eligible subjects will be randomised in a 2:1 manner to receive either somapacitan or Norditropin®

The non-inferiority margin of -2.0 cm/year is used in the trial. The randomisation will be stratified by age (<6 versus  $\geq 6$  years), gender (boys versus girls) and GH peak (< 7 versus  $\geq 7$  ng/ml) to minimize bias on the primary endpoint.

### Figure 1 Study design

## 2 Statistical Hypothesis

Hypothesis testing for the primary endpoint will be done by testing  $H_0: D \leq -2 \text{ cm/year}$  vs  $H_A: D > -2 \text{ cm/year}$ , where  $D$  is the mean treatment difference (smapacitan – Norditropin®). Non-inferiority of somapacitan will be considered confirmed if the lower boundary of the two-sided 95% confidence interval is above -2 cm/year. As only one confirmatory hypothesis is to be tested, no further control for multiplicity is needed.

### 2.1 Multiplicity Adjustment

Not applicable

### 3 Analysis Sets

The following populations are defined:

Population	Description
Full analysis set (FAS)	All subjects randomised. Exclusion of data from analyses should be used restrictively, and normally no data should be excluded from the FAS. Subjects will be analysed according to the randomised treatment
Safety analysis set (SAS)	All subjects randomly assigned to trial treatment and who take at least 1 dose of trial product. Subjects are analysed according to the treatment they actually received.
Per protocol analysis set (PP)	Subjects from FAS who have not violated any inclusion/exclusion criteria and have used the randomised treatment for at least 47 weeks (for subjects receiving somapacitan) or 329 days (for subjects receiving Norditropin) corresponding to 90% of the planned exposure. Subjects are analysed according to the treatment they actually received.

The subjects or observations to be excluded, and the reasons for their exclusion must be documented before unblinding. The subjects and observations excluded from analysis sets, and the reason for this, will be described in the CTR. Two observation periods are defined:

- on-treatment: from first administration and up until last trial contact, visit 7 or 14 days after last administration, whichever comes first
- in-trial: from first administration and up until last trial contact or visit 8, whichever comes first

Analysis based on the 'in-trial' observation period is to be viewed as supplemental analysis to the analysis based on the 'on-treatment' analysis.

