# **7 Discontinuation of trial treatment and subject discontinuation/withdrawal**

Treatment of a subject may be discontinued at any time during the trial at the discretion of the investigator for safety, behavioural, compliance or administrative reasons.

Efforts must be made to have the subjects, who discontinue trial product, attend the planned visit schedule until visit 7 to collect the required data for the analysis. Only subjects who withdraw consent will be considered as withdrawn from the trial. Subjects must be educated about the continued scientific importance of their data, even if they discontinue trial product.

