## **7.1 Discontinuation of trial treatment**

A subject who does not fulfil the eligibility criteria (inclusion/exclusion criteria) must not be randomised. Randomisation in violation of any of the eligibility criteria is a Good Clinical Practice (GCP) non-compliance and must be reported to the sponsor without delay. This will be handled as an important protocol deviation, and the independent ethics committee (IEC)/ institutional review board (IRB) and regulatory authorities must be notified according to local requirements. If there are no safety concerns, trial treatment may be continued or resumed at the discretion of the investigator after agreement with the sponsor's global medical expert.

The trial product must be discontinued, if any of the following applies for the subject:

1. Safety concern related to trial product or unacceptable intolerance
2. Simultaneous use of an approved or non-approved investigational medicinal product in another clinical trial
3. Tumour development

See the flowchart [1.2](#) for data to be collected at the time of treatment discontinuation (early discontinuation visit) and follow-up and for any further evaluations that need to be completed.

The purpose of the follow-up visit is to collect information about adverse events. For convenience of the subject the follow up visit can be performed as a telephone contact. The follow up visit should be performed as a site visit for subjects with an ongoing injection site reaction at visit 8.

The primary reason for discontinuation of trial product must be specified in the end-of-treatment-form in the CRF, and final drug accountability must be performed. A treatment discontinuation session must be made in the IWRS.

If a subject discontinues treatment prior to visit 7, Visit 7A should be performed at least 7 days after the last dose of trial product and prior to starting treatment with marketed product. The follow up visit should be performed 30 days after the last dose of trial product.

Although the treatment has been discontinued, the subject will continue to follow the planned visit schedule until visit 7 (52 weeks).

If the subject or family refuse to attend planned visit schedule, then efforts should be made for the subject to attend visit 7 as it is the primary endpoint visit.

After visit 7A the following assessments are not applicable for subjects who discontinue trial product:

- Trial drug administration
- Drug accountability
- PK and Antibody sampling

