#### **8.3.1 Time period and frequency for collecting AE and SAE information**

All AEs and SAEs must be collected from the first trial-related activity after obtaining informed consent and until the follow up visit/the end of trial visit at the time points specified in the flowchart [1.2](#).

Medical occurrences that take place or have onset prior to the time point from which AEs are collected will be recorded as concomitant illness/medical history. AE and SAE reporting timelines can be found in Appendix3, section [10.3](#). All SAEs must be recorded and reported to Novo Nordisk or designee within 24 hours, and the investigator must submit any updated SAE data to Novo Nordisk or designee within 24 hours of it being available.

Investigators are not obligated to actively seek for AE or SAE in former trial subjects. However, if the investigator learns of any SAE, including a death, at any time after a subject has been discontinued from/completed the trial, and the investigator considers the event to be possibly/probably related to the trial product or related to trial participation, the investigator must promptly notify Novo Nordisk.

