### 4.3.2 Supportive Secondary Endpoints

#### Table Efficacy

Endpoint title	Time frame	Unit
Change in bone age	From visit 1 to week 52	Years
Change in Height Standard Deviation Score	From baseline (week 0) to week 52	-10 to +10
Change in Height Velocity Standard Deviation Score	From baseline (week 0) to week 52	-10 to +10

The efficacy endpoints will be analysed based on the 'on-treatment' observation period as well as the 'in-trial' observation period within the trial period (52 weeks of treatment).

Height SDS will be derived using Chinese general population standards and HV SDS will be derived using Prader standards as reference data.

The formula to calculate height SDS is as below:

$$\text{Height SDS} = ((\text{Height} / M)^{\text{L-1}}) / (\text{L} * \text{S})$$

Height: height at the time of assessment,

L: The sex and age-specific power in the Box-Cox transformation,

M: The sex and age-specific median,

S: The sex and age-specific generalized coefficient of variation

The Chinese standards data contained three heights in cm corresponding to the median and plus/minus 2 SD for ages 0 to 18 years every six month, separately for girls and boys. Using these data as input, LMS values were calculated using the LMSfit function in R4.2.0 at these ages.

With the calculated LMS values as input the smooth.spline function with degrees of freedom 10 for L, 15 for M and 25 for S was used to obtain smoothed monthly estimates of LMS, separately for girls and boys. Finally, height SDS was calculated using above formula based on the smoothed monthly estimates.

Change in height SDS and HV SDS will be analysed using the same analysis model as was used for analysing the primary endpoint for the primary estimand except for using baseline height SDS and baseline HV SDS, respectively, as a covariate in the model instead of baseline height. The estimate for the treatment difference at week 52 will be reported with corresponding 95% CI and p-value.

Bone age will be analysed using an ANCOVA model on bone age/chronological age assessed at week 52 and the model will include treatment, sex, age group, GH peak group and sex by age group

interaction term as factors and baseline bone age/chronological age as a covariate. The treatment difference estimate will be reported with corresponding 95% CI and p-value.

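### For a child who stops treatment early, the in-trial period as written can close at visit 8, before week 52, so the supplemental in-trial analyses lose the week-52 data

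*SAP*

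**What the plan says.** SAP section 3 and Protocol 9.3 give the same definition: "in-trial: from first administration and up until last trial contact or visit 8, whichever comes first". Both call the in-trial analysis supplemental to the on-treatment one. The on-treatment period ends at the earliest of last trial contact, visit 7 and 14 days after the last administration.

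For a child who stops before visit 7, Protocol 7.1 says: "The follow up visit should be performed 30 days after the last dose of trial product". It identifies this as visit 8, and the flowchart gives it a +5 day window. Its role is narrow: "The purpose of the follow-up visit is to collect information about adverse events".

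The child nevertheless stays in the trial. Protocol section 7 asks for efforts to have such children "attend the planned visit schedule until visit 7 to collect the required data for the analysis", and 7.1 repeats that they remain on the schedule to week 52. A list in 7.1, introduced by "After visit 7A the following assessments are not applicable for subjects who discontinue trial product", names what stops. Height, the bone-age X-ray, IGF-I/IGFBP-3 and glucose metabolism are not on it.

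SAP 4.3.2 analyses the secondary efficacy, PD and glucose endpoints on both the on-treatment and the in-trial periods. Neither document gives early stoppers a separate in-trial rule.

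**The concern.** For a child who completes treatment, visit 8 follows visit 7, so ending at visit 8 is harmless. For an early stopper the order can reverse: visit 8 is tied to the last dose and visit 7 to the calendar. The rule then closes the period at a safety follow-up contact, and the week-52 measurements that sites were asked to obtain fall outside it.

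At stake is what the in-trial analysis adds. The primary analysis disregards data after discontinuation, the on-treatment period ends 14 days after the last dose, and the per-protocol set requires 47 weeks or 329 days of treatment. For a child who stops well before that, the in-trial analysis is the remaining planned place for week-52 efficacy, PD and glucose values.

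The loss differs by endpoint:
- In the MMRM analyses (height SDS, HV SDS, IGF-I SDS, IGFBP-3 SDS) the child still contributes earlier visits.
- The bone-age ANCOVA uses the week-52 value, and the SAP gives no rule for substituting an earlier one, so the child drops out.
- The descriptive summaries of fasting plasma glucose and HbA1c lack the child's week-52 change.

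**Working it through.** **Inputs.** Visit 7 is at 52W+5D, window ±1 day (flowchart). Visit 8 is 30 days after the last dose (Protocol 7.1), window +5 (flowchart). On-treatment ends 14 days after the last dose (SAP 3). Visit 5 is at 26W+1D and visit 6 at 39W (flowchart). The proportion with no week-52 data or an early stop is 10% of 108, randomised 2:1 (SAP 5).

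**The plan's own figure.** SAP 5 gives 94% power at SD 2.6. A one-sided t-test at 2.5% with margin 2.0 and 10% of subjects removed (64.8 and 32.4) gives 94.3%. This figure does not involve the in-trial period.

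**When a visit is lost.** A child who attends visit 7 after visit 8 has a last trial contact later than visit 8, so the earlier of the two is visit 8. A visit on day V is then outside the period if last dose + 30 < V, or last dose + 35 < V when the full window is used.

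| Visit | Nominal day | Lost if last dose is on or before (+30) | (+35) |
|---|---|---|---|
| 5 | 26×7+1 = 183 | 152 | 147 |
| 6 | 39×7 = 273 | 242 | 237 |
| 7 | 52×7+5 = 369 | 338 (week 48.3) | 333 (week 47.6) |

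The ±1 day window for visit 7 moves its cut-offs to days 337–339 and 332–334. If visit 7 is late by d days, they become 338 + d and 333 + d. SAP 4.2.3.2 anticipates late week-52 visits, so the nominal range is not a ceiling.

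**Examples.**
- Last dose on day 182 (week 26): visit 8 on days 212–217; visits 6 and 7 are lost.
- Last dose on day 273 (week 39): visit 8 on days 303–308; visit 7 comes 61–66 days too late.
- Last dose on day 336 (week 48): visit 8 on days 366–371; borderline.
- Last dose on day 350 (week 50): visit 8 on days 380–385; visit 7 is kept.

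**What in-trial adds to on-treatment.** When visit 8 sets the end, the in-trial period is longer by 30 − 14 = 16 days, or 35 − 14 = 21 days. Visit 7 is on-treatment if last dose + 14 ≥ 369, that is, last dose on day 355 or later. It is in-trial but not on-treatment only for a last dose on days 339–354 (16 days), or 334–354 (21 days) with the full window.

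**How many children.** 0.10 × 108 = 10.8 (0.10 × 72 = 7.2 somapacitan; 0.10 × 36 = 3.6 Norditropin). This planning proportion combines children with no week-52 data, who lose no week-52 value through this rule, with children who stop early but attend.

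**The case against.** The strongest reply is that the intent is plain. SAP 4.3.2 describes the efficacy runs as using the in-trial "observation period within the trial period (52 weeks of treatment"), early stoppers are brought back to visit 7 so that their data can be analysed, and SAP 3 says data should normally not be excluded from the full analysis set. This stands as evidence of loose wording rather than a deliberate choice. It does not rescue the rule: a limit to 52 weeks cannot extend a period that has already closed, and the glucose and PD text in SAP 4.3.2 does not carry the phrase.

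Second, the timing of visit 8 is less exact than the day counts suggest. The synopsis and Protocol 4.1 speak of a minimum of 30 days of follow-up, and the text of the flowchart footnote on visit 8 was not available to me and should be checked. If visit 8 is held k days after the last dose, the cut-off for visit 7 is day 368 − k, so a later visit 8 shrinks the problem. Somapacitan is also weekly, so a 16- or 21-day span holds only two or three planned doses. The cut-offs are approximate; the reversal of the two visits for earlier stops is not in doubt under Protocol 7.1.

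Third, a reader might infer that the in-trial analyses are the only planned ones that could use week-52 data after an early stop. That is too broad: a last dose on day 355 or later leaves a nominal visit 7 inside the on-treatment period.

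Fourth, a reader might infer that adverse events are lost too. The documents do not settle this. Protocol 7.1 does not list general adverse events among the assessments that stop, but Protocol 8.3.1 collects them "until the follow up visit/the end of trial visit", which for an early stopper may mean visit 8. No loss can be claimed until that is clarified.

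**Conclusion.** The definition is wrong as written for children whose last dose is more than about 30 to 35 days before visit 7. Their week-52 values, and for earlier stops visits 5 and 6 as well, fall outside the in-trial period. For them the in-trial and on-treatment analyses are nearly the same. The conclusion rests on a literal reading of SAP 3 and on visit 8 being held when Protocol 7.1 says.

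The consequence is minor. It is confined to supplemental analyses of supportive endpoints. Two stronger readings should be resisted:
- That non-inferiority is at risk. The primary analysis disregards data after discontinuation and uses the on-treatment period (SAP 4.2 and 4.2.2), so its estimate, power and conclusion do not depend on this definition.
- That at most 11 children are affected. The 10% is an expectation from phase 2, not a bound. Because it includes children with no week-52 data, the number affected is probably smaller and could be zero, but the documents do not cap it.

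**What to change.** In SAP 3, for the efficacy, PD and glucose analyses, keep the start of the in-trial period and end it at the earlier of (a) last trial contact and (b) the later of visit 7 and visit 8. Any attended visit 7 is then included, completers are unchanged, and children who withdraw or are lost to follow-up are covered by (a).

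Simply deleting visit 8 from the definition would be a poorer repair. Last trial contact is not defined, and antibody follow-up (Protocol 8.7) or SAE follow-up to final outcome (Protocol 8.3.3) could carry the period past visit 8, even for completers.

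For the adverse-event summaries, state in SAP 4.5.2 whether collection for early stoppers ends at visit 8 or visit 7, in line with Protocol 8.3.1, and end the in-trial period there. Otherwise the adverse-event rates could include time in which no events were collected.

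Record the change in SAP 4.8, which now reports none. SAP 1.0 was written before unblinding. SAP 2.0, dated 15 December 2023, describes the height SDS calculation in the past tense and does not give the unblinding status. State that status, and label the change post hoc if it follows unblinding.

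The cost is a revised definition in SAP 3, an entry in SAP 4.8 and a sentence in SAP 4.5.2, with no new data, visits or models. Align Protocol 9.3 if the protocol is amended for other reasons. An amendment needs authority and ethics approval (Protocol 10.1.1) and is not worth making for this alone.
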